4.1 OVERALL DESIGN

An overview of the study design is provided in Section 1.2.

Study NP40435 is a first-in-human, open-label, multicenter, Phase I multiple-ascending dose (MAD) study of single agent RO7121661. The study consists of 2 parts (A and B):

- Part A (RO7121661 Dose Escalation): To determine the MTD and/or RDE based on safety, tolerability, PK, and/or the PD profile of escalating doses of RO7121661 every 2 weeks (Q2W). If for specific cleared cohort(s) the safety, PK and/or RO and/or the biomarker profile need to be further characterized, additional participants, potentially enriched in certain indications and/or characteristics, may be enrolled.
- Part B (RO7121661 Tumor-Specific Expansion Cohorts): To evaluate anti-tumor activity of the RDE of RO7121661 from Part A (2.1 g Q2W) and to confirm safety and tolerability in participants with selected tumor types. B1, B2, B4 and B5 expansions may be staggered, sequential or concurrent. Part B3 will not proceed prior to generation of data from the initial CPI experienced indication(s):
 - Part B1: CPI experienced second line and beyond metastatic melanoma
 - Part B2: CPI and platinum experienced second or third line PD-L1 positive NSCLC
 - Part B3: PD-L1 positive, CPI naïve, first line NSCLC
 - Part B4: CPI-naïve SCLC with prior failure of, progression on, or intolerance to standard therapy
 - Part B5: CPI-naïve ESCC

Part A of the study will enroll participants with solid tumors who have progressed on a cancer therapy or who are not amenable to standard of care. At least DLT evaluable participants will be enrolled in each cohort during the dose escalation (see Section 4.1.3). Dose escalation will be carried out according to a modified continual reassessment method (mCRM) with escalation with overdose control (EWOC) design, with the aim of identifying the MTD/RDE of RO7121661.

Since RO7121661 will be administered Q2W in Part A, the cycle length will be defined as 14 days. The maximum total number of participants in the dose escalation portions of Part A1 will be approximately DLT evaluable participants on a Q2W schedule. A dose cohort can be extended to enroll additional participants (approximately), potentially enriched in certain tumor types and/or characteristics to confirm safety, PK and/or RO and/or the biomarker profile.

Part B1 and/or B2 and/or B4 and/or B5 may commence upon completion of Part A. The starting dose of RO7121661 for Part B is 2.1 g Q2W as derived from the RDE in Part A

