The DLT period is 21 days from Day 1/Cycle 1 to Day 7/Cycle 2. If there is a delay in Cycle 2 treatment the DLT period should be adjusted to cover Day 7/Cycle 2 up to a maximum of 35 days, since the maximum dose delay allowed is 14 days.

Once at least participants per cohort are DLT-evaluable, the logistic regression model will be updated with the treatment outcome (i.e., the occurrence of DLT). Thus, a new estimate of the MTD (defined as the dose with the highest probability that the DLT rate is within the target of 20-35% and a relatively low probability <25% that the DLT rate is above 35%) will be derived. In addition, the model will recommend a dose for the new cohort of participants, with the EWOC recommendation being either the new estimate of the MTD or the highest allowable dose based on pre-specified safety constraints (e.g., maximum increments), whichever is lower.

Built in safety constraints are in place to prevent exposing participants to undue risk of toxicity. For instance, in the absence of DLT, the maximum allowable dose-increment will be 200% (i.e., next dose could be as high as 3-fold the previous dose) for dose-levels <700 mg and 100% (i.e. 2-fold) for dose-levels \ge 700 mg. In addition, in case of one event meeting DLT criteria in a dose-level, the maximum allowable dose

increment becomes 100% (i.e. 2-fold); while in the presence of 2 DLTs an increment of 50% is allowed (i.e. 1.5-fold). For further information see Table 1 in Appendix 10.

The dose escalation decision and selection of the dose for the next cohort, guided by the mCRM EWOC recommendation, will also take into account an overall review of safety and available PK and/or PD data as well as any additional data. Subject to clinical judgment, and upon agreement between the Sponsor and the Investigators on the next dose-escalation step, the new cohort can then be opened for enrollment.

The design will continue as described, until one of the pre-defined stopping criteria is satisfied (see Section 4.1.4), or the RDE has been defined, whichever comes first.

4.1.3 **Dose Limiting Toxicities**

For the purpose of this study, a DLT will be defined as any of the following events attributed to RO7121661 (i.e., related to RO7121661) and occurring during the DLT window:

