A DLT is defined as a clinically significant AE (classified according to the National Cancer Institute Common Terminology Criteria for Adverse Events [NCI CTCAE] v.5.0, as applicable) or significant laboratory abnormality: 1) occurring during the DLT assessment period of 21 days from the start of the first RO7121661 administration; 2) considered to be related to study treatment RO7121661 by the Investigator and; 3) is not attributed to disease progression or another clearly identifiable cause.

Investigators are encouraged to perform additional tests to determine the underlying etiology and most appropriate attribution.

For the purpose of this study the following AEs are considered DLTs:

- Hematological toxicities:
 - Grade 4 neutropenia (ANC $< 0.5 \times 10^9$ /L) lasting > 5 days.
 - Grade ≥ 3 febrile neutropenia associated with single body temperature > 38.3°C or sustained body temperature ≥ 38°C for > 1 hour, and/or with infection.
 - Grade 4 thrombocytopenia lasting>48 hours.
 - Grade 3 thrombocytopenia associated with bleeding episodes requiring a platelet transfusion.
 - Grade 4 anemia
 - Grade ≥ 3 anemia with hemolysis
- Any non-hematological toxicity of Grade ≥ 3 including:
 - Any Grade 3 immune-mediated AE.
 - Grade 3 hyperbilirubinemia lasting for > 48 hours or Grade 4 hyperbilirubinemia.

- Grade≥3 AST or ALT elevations with hyperbilirubinemia of Grade≥2.
- Grade 4 AST or ALT elevations.
- Grade ≥ 3 nausea, vomiting, or diarrhea despite maximal supportive treatment.
- Grade ≥ 3 non-hematological laboratory abnormality requiring medical treatment/intervention or hospitalization.
- The following Grade ≥ 3 non-hematological toxicity are exceptions for consideration as DLTs:
 - Alopecia (any grade).
 - Grade 3 nausea or vomiting that resolves to Grade ≤ 1 with or without supportive therapy within one week.
 - Grade 3 hypophosphatemia resolved within one week.
 - Grade ≥3 fatigue/asthenia that resolves to Grade ≤2 within one week.
 - Grade 3 anorexia or constipation.

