Failure to recover from any RO7121661-related toxicity that results in a dose-delay of the next scheduled administration of more than 14 days is defined as a DLT.

4.1.4 **Stopping Rules Criteria**

Part A Dose Escalation 4.1.4.1

The algorithm of the mCRM with EWOC will propose to stop the dose escalation under the following circumstances:

- The maximum sample size of evaluable participants has been reached **OR**
- Enough information on MTD has been achieved (i.e., at least a minimum of participants enrolled and at least participants have been accrued near the MTD dose - where near is defined as differing from the MTD by at most 15% - and the probability that the MTD dose lies within the target toxicity interval is above 50%)

OR

The maximum dose has been tested and is considered safe (i.e., at least a minimum of participants have been accrued at the maximum dose or near differing from the maximum dose by at most 5% - and it is at least 50% likely that the probability of a DLT for that maximum dose is below 20%).

Due to the exploratory nature of this clinical study, any part of its conduct can be discontinued at any time at the discretion of the Sponsor. This will not constitute a premature termination of the study. The Sponsor will notify the Investigators and Health Authorities if the study is discontinued or the development program is terminated.

4.1.5 **Communication Strategy**

For Part A: Upon completion of all screening evaluations and confirmation that a participant has met all inclusion and exclusion criteria, investigator sites will contact the Sponsor to confirm the dose, participant number and cohort assignment via a Confirmation of Enrollment form (ESF). This will guarantee that the Sponsor is notified

prior to the administration of RO7121661 to any participant. Then sites will need to contact the interactive response technology system (IRT) vendor who will generate confirmation of participant number, dose and cohort assignment. The IRT participant number should be generated prior to first dose.

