6.6 DOSAGE MODIFICATION

Instructions for RO7121661 administration, change of infusion rate, and interruption of infusion are provided in Section 6.1 and Section 7.

Participants who experience toxicities fulfilling the definition of a DLT in the first cycle, or DLT-equivalent toxicities in subsequent cycles should be discontinued from study treatment. Nevertheless, the Investigators, after discussion with the Sponsor, will have the option to reduce the dose of RO7121661 to the previous tolerated dose level, if participant is deemed to be deriving clinical benefit.

A delay of RO7121661 administration for up to two cycles, will be acceptable to allow for resolution of toxicity to NCI CTCAE Grade ≤ 2 for hematological toxicities or Grade ≤ 1 for non-hematological toxicities (with the exception of a toxicity considered as non-RO7121661 related).

If the toxicity does not resolve to NCI CTCAE Grade ≤ 2 for hematological toxicities or ≤ 1 for non-hematological toxicities and the participant is unable to resume treatment with RO7121661 after this time (omission of two doses), no additional doses will be administered and the participant will be withdrawn from study treatment, unless the participant exhibits a clinical benefit and this is discussed by the Investigator and the Medical Monitor. It should be noted that infusions/cycles not occurring at the anticipated schedule, are considered as delayed, not missed.

Further dose-reductions may be implemented once safety and toxicity data from the dose-escalation have been evaluated.

For participants with documented liver metastasis and elevated liver function test (LFT) results at baseline, further elevations of LFT results may not require dose interruptions if there are no progressive changes in the ALT and/or AST (less than a doubling) and if there are no progressive elevations in total bilirubin or international normalized ratio (INR).

Investigators are encouraged to contact the Sponsor for further guidance if needed. After Cycle 1 is completed, dose modifications should be discussed with the Sponsor. In these instances, a confirmation with the Sponsor is requested and documentation in the eCRF is requested. Treatment delays of up to 3 days due to logistical considerations (e.g., center closure for holiday) are generally acceptable and do not need to be discussed with the Sponsor. In no instance are cycles shorter than 14 days of duration (i.e. Q2W) allowed in this study.

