- No decline in ECOG performance status.
- Absence of rapid progression of disease or of progressive tumor at critical anatomical sites (e.g., cord compression) requiring urgent alternative medical intervention.

Participants who discontinue study treatment will be asked to return to the clinic for an End-of-Treatment visit (see Section 8.10.3) and may undergo follow-up assessments (see Section 8.10.4). The primary reason for study treatment discontinuation should be documented on the appropriate eCRF.

Participants who discontinue study treatment prematurely may be replaced for the following reasons to ensure adequate numbers of evaluable participants:

 Participant who withdraws from the study prior to the treatment start may be replaced and will not be entered into the database.

- Participants who fail to complete their DLT assessment period because of non-drugrelated reasons.
- In the case of a major protocol violation participants will be excluded from the MTD/DLT analysis but might continue the treatment if deemed beneficial, and if there is no safety concern associated with the protocol violation criteria and according to clinical judgment.

Participants will be treated until disease progression, loss of clinical benefit, unacceptable toxicities, or withdrawal from treatment for other reasons, or death.

7.1.1 Temporary Interruption

Before permanently discontinuing study treatment (regardless of whether initiated by the participant, the Investigator or Sponsor), an interruption should be considered. Participants, who have temporarily interrupted study treatment, should be considered to re start as soon as medically justified in the opinion of the Investigator.

Dose interruptions for reason(s) other than toxicity, such as surgical procedures, may be allowed. The acceptable length of interruption will depend on the *discussion* between the Investigator and the Medical Monitor.

In case of toxicity requiring RO7121661 treatment to be put on hold, the study treatment should only re-start once the toxicities have resolved to NCI CTCAE Grade ≤ 2 for hematological toxicities or Grade ≤ 1 for non-hematological toxicities. Participants who do not recover from drug-related toxicities after omission of up to 2 doses (delay of 4 weeks in the Q2W schedule) of RO7121661 and who in the opinion of the Investigator are not receiving clinical benefit from RO7121661 treatment, should be permanently discontinued from the study.

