Table 1 Management Guidelines for Pulmonary Events, Including Pneumonitis

Event	Management
Pulmonary event, Grade 1	 Continue RO7121661 and monitor closely. Re-evaluate on serial imaging. Consider patient referral to pulmonary specialist.
Pulmonary event, Grade 2	 Withhold RO7121661 for up to 12 weeks after event onset. a Refer patient to pulmonary and infectious disease specialists and consider bronchoscopy or BAL. Initiate treatment with 1–2 mg/kg/day oral prednisone or equivalent. If event resolves to Grade 1 or better, resume RO7121661. b If event does not resolve to Grade 1 or better while withholding RO7121661, permanently discontinue RO7121661 and contact Medical Monitor. c For recurrent events, treat as a Grade 3 or 4 event.
Pulmonary event, Grade 3 or 4	 Permanently discontinue RO7121661 and contact Medical Monitor. Bronchoscopy or BAL is recommended. Initiate treatment with 1–2 mg/kg/day oral prednisone or equivalent. If event does not improve within 48 hours after initiating corticosteroids, consider adding an immunosuppressive agent. If event resolves to Grade 1 or better, taper corticosteroids over ≥ 1 month.

BAL = bronchoscopic alveolar lavage.

- a RO7121661 may be withheld for a longer period of time (i.e., > 12 weeks after event onset) to allow for corticosteroids (if initiated) to be reduced to ≤ 10 mg/day oral prednisone or equivalent. The *Investigator determines an* acceptable length of the extended period of time. The Medical Monitor is available to the *Investigator to advise and answer questions in this regard*.
- b If corticosteroids have been initiated, they must be tapered over≥1 month to ≤10 mg/day oral prednisone or equivalent before RO7121661 can be resumed.

HEPATIC EVENTS

Immune-mediated hepatitis may be associated with the administration of RO7121661. Eligible patients must have adequate liver function, as manifested by measurements of total bilirubin and hepatic transaminases, and liver function will be monitored throughout study treatment. Management guidelines for hepatic events are provided in Table 2.

Patients with right upper-quadrant abdominal pain and/or unexplained nausea or vomiting should have liver function tests (LFTs) performed immediately and reviewed before administration of the next dose of study drug.

For patients with elevated LFTs, concurrent medication, viral hepatitis, and toxic or neoplastic etiologies should be considered and addressed, as appropriate.

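### Sections 6.6 and 7.1.1 conflict with Appendix 6 on stopping, holding and resuming treatment after some of the same toxicities, and no text says which governs

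*Combined protocol and SAP*

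**What the plan says.** - **Section 4.1.3** lists "Any Grade 3 immune-mediated AE" among the dose-limiting toxicities (DLTs), subject to exceptions. One exception is Grade 3 diarrhea, colitis or enteritis that falls to Grade 1 or lower within a week without fever or dehydration. The section adds that failure to recover from a related toxicity that leads to a "dose-delay of the next scheduled administration of more than 14 days is defined as a DLT".
- **Section 6.6** says that participants with a DLT in the first cycle or "DLT-equivalent toxicities in subsequent cycles should be discontinued from study treatment". The one alternative is a lower, previously tolerated dose level, after discussion with the Sponsor, if the participant is deriving clinical benefit. The section also accepts a delay of up to two cycles for toxicity to resolve. If it has not resolved and treatment cannot restart "after this time (omission of two doses), no additional doses will be administered and the participant will be withdrawn from study treatment", unless there is clinical benefit and the case is discussed with the Medical Monitor.
- **Section 7.1.1** stops those who have not recovered "after omission of up to 2 doses (delay of 4 weeks in the Q2W schedule" and who, in the Investigator's opinion, are not benefitting. It allows restart after a longer hold if the Investigator judges benefit likely. The stop it describes is from the study, whereas Section 6.6 withdraws from treatment.
- **Section 8.3.8.2** says Grade 3 immune-mediated toxicity generally leads to suspension, and sends the reader to Appendix 6.
- **Appendix 6** tells sites, for most events that lead to a hold, "Withhold RO7121661 for up to 12 weeks after event onset", with a footnote allowing longer so that steroids can be tapered. Treatment resumes at Grade 1 or better.

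**The concern.** These sections decide who stays on drug after toxicity. If two of them give different orders for one event, and neither is said to prevail, the outcome depends on which page the site consults. At stake are participant safety, the amount of drug received, and the planned summaries of premature withdrawal from treatment and of dose interruptions, which would then partly reflect how sites read the protocol.

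**Working it through.** **Hold length**

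1. Cycle length, Section 4.1: "the cycle length will be defined as 14 days".
2. The plan's own figure: 2 omitted doses × 14 days = 28 days = 4 weeks. This reproduces Section 7.1.1.
3. Appendix 6: 12 weeks × 7 = 84 days, or 84 / 14 = 6 cycles.
4. Ratio of the nominal limits: 84 / 28 = 3.
5. The clocks differ. Appendix 6 counts from event onset; the 4 weeks are a delay of the scheduled dose. An event starting 0 to 14 days after the last dose has 14 + 28 − (0 to 14) = 28 to 42 days from onset before the Section 6.6 limit. On that common clock the ratio is 84 / 42 = 2 to 84 / 28 = 3.
6. The conflict covers participants whose toxicity is still unresolved when the 4 weeks end and who are not judged to be benefitting or likely to benefit. For an event present on the due dosing day, the contested period is days 29 to 84.

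**Grade 3 immune-mediated events**

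| Grade 3 event | Sections 4.1.3 and 6.6 (outside the DLT exceptions) | Appendix 6 |
|---|---|---|
| Diarrhea/colitis, hypophysitis, pancreatitis, dermatologic, myositis | Should discontinue; reduced dose possible with benefit, after Sponsor discussion | Withhold; resume at Grade 1 or better |
| Pulmonary, hepatic, ocular, renal, neuropathy | Same | Permanently discontinue |

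The first row conflicts; in the second both texts point to stopping. The resume instructions in the first row carry no benefit condition and no dose reduction, although the Appendix's introduction asks the Investigator to weigh benefit and risk in general. Symptomatic adrenal insufficiency (Grade 2–4) follows the first-row pattern, with stable replacement therapy as an added condition.

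Example: Grade 3 colitis takes ten days to reach Grade 1, so it misses the one-week exception. If no benefit is yet judged, Section 6.6 says stop and Appendix 6 says resume. If benefit is judged, the texts still differ on dose: Section 6.6 offers a reduced one, and Appendix 6 mentions no reduction.

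**Within the body text**

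Under Section 4.1.3, a delay of 15 days or more because a related toxicity has not recovered is a DLT. Section 6.6 says such toxicity should lead to discontinuation, yet accepts delays of up to 2 × 14 = 28 days. Days 15 to 28 therefore carry two instructions.

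**The case against.** The best defence is that the body text gives a general rule and Appendix 6 the event-specific one. Section 8.3.8.2 directs immune-mediated events to Appendix 6, Section 7.1 cross-refers to it, and Section 8.3.8 lets the Investigator depart from the guidance in consultation with the Medical Monitor. Appendix 6 even permits rechallenge after its permanent-stop criteria are met, if the participant is benefitting and has fully recovered. Section 6.6 is worded as what should happen, and both it and Section 7.1.1 have benefit exceptions.

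Much of this stands. A participant judged to be benefitting can often continue under either reading. But the specific-over-general rule is written nowhere. The amendment rationale says Appendix 6's interruption sections were removed as redundant with Sections 6.6 and 7.1.1, which if anything points the other way. The exceptions also differ: Section 6.6 wants benefit exhibited and discussed with the Medical Monitor, Section 7.1.1 accepts likely benefit on the Investigator's judgment, and the Appendix 6 resume rows set no such test.

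A reader might infer more than the text supports:

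- **That 14 days is a third hold limit, giving a 6-fold range (84 / 14).** Section 4.1.2 and Table 7 do say "since the maximum dose delay allowed is 14 days", but to explain why the DLT window can extend to 21 + 14 = 35 days. In Section 4.1.3 the figure classifies a DLT. It reaches Section 6.6 only through the DLT wording.
- **That the steroid taper of at least a month in Appendix 6 makes restart impossible under Section 6.6.** The stop clauses in Sections 6.6 and 7.1.1 address unresolved toxicity. Someone who has reached Grade 1 and is only tapering does not meet them.
- **That no exception can apply before the first on-study scan at 8 weeks.** Section 7.1.1 rests on the Investigator's judgment of likely benefit and requires no scan.

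**Conclusion.** The plan is wrong as written on three points: discontinue against resume for five kinds of Grade 3 immune-mediated event, outside the DLT exceptions; 28 against 84 days for unresolved toxicity in participants not judged to be benefitting or likely to benefit; and two instructions for related-toxicity delays of 15 to 28 days. The mismatch between leaving treatment (Section 6.6) and leaving the study (Section 7.1.1) adds uncertainty about follow-up.

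The conclusion assumes that Section 6.6 means what it says about DLT-equivalent toxicity and, as its wording carries no such limit, is not confined to Part A. How many participants would be affected cannot be estimated, because the documents give no rates for these events.

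Different handling at different sites is a foreseeable risk; the documents do not show that it has happened. A reader might also infer bias in PFS or duration of response. That is not demonstrated. Section 9.4.2 ends PFS at progression or death, and the notes to the Table 1 schedule continue scans until progression or treatment discontinuation, whichever is later. A toxicity stop does not by itself cut PFS short.

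**What to change.** Reconcile Sections 4.1.3, 6.6, 7.1.1, 8.3.8.2 and the Appendix 6 tables:

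- State which text governs immune-mediated events and which governs other toxicity.
- Make the Grade 3 instruction and the hold limit agree under that order of precedence, and say from which date the hold is counted.
- Settle how the more-than-14-day DLT criterion relates to the two-cycle delay that Section 6.6 accepts.
- Use one benefit test for the exceptions, or say why the tests differ.
- Say whether a participant stopped for toxicity leaves treatment only or also the study.

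The cost is protocol wording, with no change to sample size or analysis. Which hold length or stopping rule to adopt is a clinical decision for the Sponsor and Investigators; none is proposed here.
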